## **4.2 Rationale**

### **4.2.1 Rationale for the Trial and Selected Subject Population**

Details regarding specific benefits and risks for subjects participating in this clinical trial may be found in the accompanying IB and Informed Consent documents.

This is a multicenter, nonrandomized, single-cohort trial of pembrolizumab (MK-3475) in subjects with recurrent and/or metastatic head and neck squamous cell carcinoma. Trials evaluating pembrolizumab (MK-3475) in head and neck cancer have demonstrated clinical activity in subjects with recurrent and/or metastatic disease. Refer to Section 4.1.3, Ongoing Clinical Trials, for results from the Phase Ib study of pembrolizumab in patients with HPV-negative and HPV-positive head and neck cancer (KEYNOTE 012).

Participation in this trial will be dependent upon supplying a newly obtained core or excisional biopsy of a tumor lesion. The tissue specimens will be evaluated at a central laboratory for expression status of PD-L1 in a retrospective analysis, thus tissue availability, but not high biomarker expression is required for study entry. Therefore subjects will be enrolled onto this trial irrespective of PD-L1 expression (including subjects whose tumors do not express PD-L1). If emerging biomarker data from on-going subjects being treated with pembrolizumab (MK-3475) in KEYNOTE 012 does not confirm the clinical utility of the PD-L1 biomarker in newly obtained tumor tissue to predict response to pembrolizumab (MK-3475), the newly obtained tumor sample may become optional, and may be substituted by an archival tumor tissue sample.

### **4.2.2 Rationale for Dose Selection/Regimen/Modification**

An open-label Phase I trial (KEYNOTE 001) is being conducted to evaluate the safety and clinical activity of single agent pembrolizumab (MK-3475). The dose escalation portion of this trial evaluated three dose levels, 1 mg/kg, 3 mg/kg, and 10 mg/kg, administered every 2 weeks (Q2W) in subjects with advanced solid tumors. All three dose levels were well tolerated and no dose-limiting toxicities were observed. This first in human study of pembrolizumab (MK-3475) showed evidence of target engagement and objective evidence of tumor size reduction at all dose levels (1 mg/kg, 3 mg/kg and 10 mg/kg Q2W). No MTD has been identified.

In KEYNOTE 001, two randomized cohort evaluations of melanoma subjects receiving pembrolizumab (MK-3475) at a dose of 2 mg/kg versus 10 mg/kg Q3W have been completed, and one randomized cohort evaluating of 10 mg/kg Q3W versus 10 mg/kg Q2W has also been completed. The clinical efficacy and safety data demonstrate a lack of clinically important differences in efficacy response or safety profile at these doses. For example, in Cohort B2, advanced melanoma subjects who had received prior ipilimumab therapy were randomized to receive pembrolizumab (MK-3475) at 2 mg/kg versus 10 mg/kg Q3W. The ORR was 26% (21/81) in the 2mg/kg group and 26% (20/76) in the 10 mg/kg group (FAS). The proportion of subjects with drug-related AE, grade 3-5 drug-related AE, serious drug-related AE, death or discontinuation due to an AE was comparable between groups or lower in the 10 mg/kg group. In Cohort B3, advanced melanoma subjects (irrespective of prior ipilimumab therapy) were randomized to receive pembrolizumab (MK-3475) at 10 mg/kg Q2W versus 10 mg/kg Q3W. The ORR was 30.9% (38/123) in the 10mg/kg Q2W group and 24.8% (30/121) in the 10 mg/kg Q3W group (APaT). The proportion of subjects with drug-related AE, grade 3-5 drug-related AE, serious drug-related AE, death or discontinuation due to an AE was comparable between groups.

PK data analysis of pembrolizumab (MK-3475) administered Q2W and Q3W showed slow systemic clearance, limited volume of distribution, and a long half-life (refer to IB). Pharmacodynamic data (IL-2 release assay) suggested that peripheral target engagement is durable (>21 days). This early PK and pharmacodynamic data provides scientific rationale for testing a Q3W dosing schedule. Because Q3W dosing is more convenient for subjects, Q3W dosing will be evaluated in this protocol.

The rationale for further exploration of 2mg/kg and comparable doses of MK-3475 in solid tumors is based on: 1) similar efficacy and safety of MK-3475 when dosed at either 2 mg/kg or 10 mg/kg Q3W in melanoma patients, 2) the flat exposure-response relationships of MK-3475 for both efficacy and safety in the dose ranges of 2 mg/kg Q3W to 10 mg/kg Q3W, 3) the lack of effect of tumor burden or indication on distribution behavior of MK-3475 (as assessed by the population PK model) and 4) the assumption that the dynamics of MK-3475 target engagement will not vary meaningfully with tumor type.

The choice of the 200 mg Q3W as an appropriate dose for the switch to fixed dosing is based on simulations performed using the population PK model of MK-3475 showing that the fixed dose of 200 mg every 3 weeks will provide exposures that 1) are optimally consistent with those obtained with the 2 mg/kg dose every 3 weeks, 2) will maintain individual patient exposures in the exposure range established in melanoma as associated with maximal efficacy response and 3) will maintain individual patients exposure in the exposure range established in melanoma that are well tolerated and safe.

A fixed dose regimen will simplify the dosing regimen to be more convenient for physicians and to reduce potential for dosing errors. A fixed dosing scheme will also reduce complexity in the logistical chain at treatment facilities and reduce wastage.

#### 4.2.3 Rationale for Endpoints

##### 4.2.3.1 Efficacy Endpoints

The primary efficacy objective of this trial is to evaluate the anti-tumor activity of pembrolizumab (MK-3475) in subjects with recurrent and/or metastatic head and neck squamous cell carcinoma (HNSCC). Response rates per RECIST 1.1 [31] as assessed by the central vendor will be used as the primary response rate efficacy endpoint.

RECIST 1.1 will also be used by the local site for treatment decisions. However RECIST 1.1 will be adapted to account for the unique tumor response profile seen with treatment of pembrolizumab (MK-3475).

Immunotherapeutic agents such as pembrolizumab (MK-3475) may produce antitumor effects by potentiating endogenous cancer-specific immune responses which may be functionally anergic. The response patterns seen with such an approach may extend beyond the typical time course of responses seen with cytotoxic agents, and can manifest a clinical response after an initial increase in tumor burden or even the appearance of new lesions. Standard RECIST criteria may not provide a complete response assessment of immunotherapeutic agents such as pembrolizumab (MK-3475). Therefore, RECIST 1.1 will be used with the following adaptation, termed Modified RECIST 1.1.

If radiologic imaging shows PD, tumor assessment should be repeated  $\geq$  4 weeks later in order to confirm PD with the option of continuing treatment per below while awaiting radiologic confirmation of progression. If repeat imaging shows  $< 20\%$  tumor burden compared to nadir, stable or improved previous new lesion (if identified as cause for initial PD), and stable/improved non-target disease (if identified as cause for initial PD), PD is not confirmed. Treatment may be continued as per treatment calendar.

If repeat imaging confirms progressive disease due to any of the scenarios listed below, subjects will be discontinued from trial treatment (exception noted in Section 7.1.2.6.3). In determining whether or not the tumor burden has increased or decreased, Investigators should consider all target lesions as well as non-target lesions.

Scenarios where PD is confirmed at repeat imaging:

- Tumor burden remains  $\geq 20\%$  and at least 5 mm absolute increase compared to nadir
- Non-target disease resulting in initial PD is worse (qualitative)
- New lesion resulting in initial PD is worse (qualitative)
- Additional new lesion(s) since last evaluation
- Additional new non-target progression since last evaluation

In subjects who have initial evidence of radiological PD, it is at the discretion of the treating physician whether to continue a subject on trial treatment until repeat imaging is obtained a

minimum of 4 weeks later. This decision should be based on the clinical judgment of the subject's overall clinical condition, including performance status, clinical symptoms, and laboratory data. Subjects may receive treatment while waiting for confirmation of PD if they are clinically stable as defined by the following criteria:

- Absence of signs and symptoms indicating disease progression
- No decline in ECOG performance status
- Absence of rapid progression of disease
- Absence of progressive tumor at critical anatomical sites (e.g., cord compression) requiring urgent alternative medical intervention

When feasible, subjects should not be discontinued until progression is confirmed. This allowance to continue treatment despite initial radiologic progression takes into account the observation that some subjects can have a transient tumor flare in the first few months after the start of immunotherapy, but with subsequent disease response. Subjects that are deemed clinically unstable are not required to have repeat imaging for confirmation of progressive disease. Supportive retrospective independent review of all imaging time points will be performed for this trial using Modified RECIST 1.1.

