#### **7.1.2.6.3 Assessment of Disease**

RECIST 1.1 will be applied by the central imaging vendor as the primary measure for assessment of tumor response. Scans should be submitted to the central imaging vendor in a timely fashion. Sites should also assess tumor response and progression per modified RECIST 1.1 and this data will be collected in the clinical database. Site assessment of tumor response and progression will be used for all patient decision making in the trial.

Modified RECIST 1.1 is RECIST 1.1 adapted as follows to account for the unique tumor response seen in this class of therapeutics (refer to Section 4.2.2.1).

If radiologic imaging shows PD, tumor assessment may be repeated  $\geq$  4 weeks later at the site in order to confirm PD with the option of continuing treatment for clinically stable subjects as discussed below in [Table 6](#). Clinically stable is defined by the following criteria:

- Absence of signs and symptoms indicating disease progression
- No decline in ECOG performance status
- Absence of rapid progression of disease
- Absence of progressive tumor at critical anatomical sites (e.g., cord compression) requiring urgent alternative medical intervention

Table 6 Imaging and Treatment after 1st radiologic evidence of PD

	Clinically Stable		Clinically Unstable	
	Imaging	Treatment	Imaging	Treatment
1 st radiologic evidence of PD	Repeat imaging at $\geq$ 4 weeks at site to confirm PD	May continue study treatment at the Investigator's discretion while awaiting confirmatory scan by site	Repeat imaging at $\geq$ 4 weeks to confirm PD per physician discretion only	Discontinue treatment
Repeat scan confirms PD	No additional imaging required	Discontinue treatment	No additional imaging required	N/A
Repeat scan shows SD, PR or CR	Continue regularly scheduled imaging assessments	Continue study treatment at the Investigator's discretion	Continue regularly scheduled imaging assessments	May restart study treatment if condition has improved and/or clinically stable per Investigator's discretion

In determining whether or not the tumor burden has increased or decreased, investigators should consider all target lesions as well as non-target lesions. Subjects that are deemed clinically unstable are not required to have repeat imaging for confirmation. If radiologic progression is confirmed (by subsequent scan) then the subject will be discontinued from trial treatment.

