If radiologic progression is not confirmed, then the subject should resume/continue trial treatment and have their next scan at the regularly scheduled interval. Subjects who obtain a confirmation scan at 4 weeks do not need to undergo the next scheduled imaging assessment if it is due  $<$  4 weeks later. Imaging may be performed at the next scheduled imaging timepoint if the subject remains clinically stable.

**NOTE:** If a subject with confirmed radiographic progression (i.e. 2 scans at least 28 days apart demonstrating progressive disease) is clinically stable or clinically improved, and there is no further increase in the tumor dimensions at the confirmatory scan, an exception may be considered to continue treatment upon consultation with the Sponsor.

Imaging during the follow-up period is to be repeated every 6 weeks ( $\pm$  7 days) for the first year patients are on study and then every 9 weeks ( $\pm$  7 days) after 1 year for subjects who discontinue trial treatment for reasons other than disease progression. Follow-up scans should be continued until the subject experiences confirmed disease progression or starts a new anti-neoplastic therapy.

If imaging assessment beyond the protocol-required imaging time frame is necessary for the subject's continued participation in the follow-up phase of the study, an extended imaging schedule may be considered at the discretion of the investigator. Please refer to Section 6.1-Initial Treatment Phase and Second Course Phase (Retreatment).

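### Section 4.2.3.1 labels one kind of repeat scan both 'not confirmed' and 'confirmed' progression, and does not say which label prevails

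*Combined protocol and SAP*

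**What the plan says.** Section 8.2.3.1 points to Section 4.2.3.1 for the definition of modified RECIST 1.1. That section contains two rules for the repeat scan.

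- **Not-confirmed rule.** If the repeat scan shows less than 20% "tumor burden compared to nadir, stable or improved previous new lesion (if identified as cause for initial PD), and stable/improved non-target disease" (again, if that was the cause), then "PD is not confirmed. Treatment may be continued as per treatment calendar".
- **Confirmed rule.** If the repeat scan "confirms progressive disease due to any of the scenarios listed below, subjects will be discontinued from trial treatment (exception noted in Section 7.1.2.6.3". Five scenarios follow: (1) burden still at least 20% and "at least 5 mm absolute increase compared to nadir"; (2) worsening of the non-target disease that caused the first PD; (3) worsening of the new lesion that caused it; (4) "Additional new lesion(s) since last evaluation"; (5) "Additional new non-target progression since last evaluation".

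Section 7.1.2.6.3 attaches actions to the label. Confirmed progression means discontinuation, while "If radiologic progression is not confirmed, then the subject should resume/continue trial treatment". The same section states: "Site assessment of tumor response and progression will be used for all patient decision making in the trial". It allows an exception to discontinuation for a subject who is clinically stable or improved, whose tumor dimensions have not increased further at the confirming scan, and for whom the Sponsor has been consulted.

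**The concern.** The two rules should be complements, and they are not. The not-confirmed rule has no condition on additional new lesions or additional non-target progression, although scenarios 4 and 5 make each of these enough to confirm PD. A scan can therefore meet both rules, with treatment permitted under one and stopped under the other. Two sites following the text could treat the same scan differently.

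The label also decides whether the first PD stands as progression under modified RECIST. That criterion is used for the investigator-read PFS and response-duration summaries in Table 10 and for exploratory objective 1 in Section 3.3 (PFS by central review).

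**Working it through.** The plan states no figure on this point, so the check applies the two rules literally.

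**Readings used.** The not-confirmed sentence omits the word 'increase'; I read it as a rise of less than 20% above nadir. I take burden as the sum of target lesions, and a causal lesion as either stable/improved or worse.

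**Rule A (not confirmed):** rise < 20% and causal lesions stable or improved.
**Rule B (confirmed):** (rise ≥ 20% and ≥ 5 mm), or a causal lesion worse, or an additional new lesion or additional non-target progression.

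Three target states × two causal-lesion states × two states for anything additional gives 12 combinations:

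| Target rise from nadir | Causal lesions | Anything additional | Rule A | Rule B |
|---|---|---|---|---|
| < 20% | stable | no | met | not met |
| < 20% | stable | yes | **met** | **met** |
| ≥ 20% and ≥ 5 mm | stable | no | not met | met |
| ≥ 20% but < 5 mm | stable | no | not met | not met |
| the other 8 combinations | – | – | not met | met |

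That is 1 not confirmed only, 8 + 1 = 9 confirmed only, 1 both and 1 neither. These counts map the wording; they are not frequencies.

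**The scan that meets both rules, by example.** Target sum 50 mm at nadir, 50 mm at first PD (called because of a new lesion) and 52.5 mm at repeat. The original new lesion is stable and a second new lesion has appeared.
- Rise from nadir: (52.5 − 50)/50 = 5%, below 20%, with the causal lesion stable. Rule A is met.
- An additional new lesion is scenario 4. Rule B is met.
- Change from the first-PD scan: 52.5 − 50 = +2.5 mm, so the no-further-increase condition of the Section 7.1.2.6.3 exception fails. The exception does not reconcile the rules here. With targets unchanged or smaller it might be open, on Sponsor consultation.

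**The scan that meets neither rule.** A rise of at least 20% but under 5 mm requires 0.2 × nadir < 5 mm, so a nadir sum below 25 mm. The window is 2 to < 5 mm at nadir 10 mm, 3 to < 5 at 15, 4 to < 5 at 20, and empty at 25 or more. Example: 14 mm at nadir, 20 mm at first PD, 18 mm at repeat. The rise is 4 mm, or 4/14 = 28.6%. No scenario is met, so PD has not been confirmed.

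**Other text that might settle the overlap.** Section 7.1.2.6.3 assigns actions to the label without restating the criteria. Section 5.2.2.1 lets treatment continue after a reduction in burden from the first-PD scan; that is a treatment rule rather than a definition of confirmed PD, and it does not apply to the 50/50/52.5 mm example. No sentence sets precedence.

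**The case against.** The strongest reply is that a sensible reader resolves the overlap unaided. The not-confirmed sentence is permissive about treatment, the list is mandatory, and the list works on an any-one-suffices basis. The specific list should therefore govern. I agree that this is the likely reading, but the text does not state it, and the not-confirmed sentence assigns a label as well as a permission.

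Second, Section 4.2.3.1 tells investigators to consider non-target as well as target lesions when judging whether burden has changed. On that view, additional non-target progression may not satisfy the not-confirmed rule at all. This stands in part: the conflict is clear for an additional new lesion and less clear for additional non-target progression.

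Third, a reader might infer that the ≥ 20% but < 5 mm scan leaves sites without an instruction. The documents do not support that. A scan meeting none of the five scenarios has not confirmed PD, Section 4.2.3.1 asks that subjects stay on treatment until confirmation where feasible, Section 7.1.2.6.3 says to continue when PD is not confirmed, and Tables 4 and 6 cover a repeat scan read as SD. That case needs only a wording clean-up.

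Fourth, a reader might infer a measurable shift in PFS. Take a subject with first PD at Week 9 and a repeat scan at Week 13. Calling an overlap scan not confirmed moves progression by 13 − 9 = 4 weeks if the additional lesion counts as a new first PD at Week 13. The move is 21 − 9 = 12 weeks if the optional Week 15 scan is skipped and progression is next called at Week 21. The second needs a reader who sees a new lesion and calls nothing for eight weeks. Both illustrate one subject; neither estimates an effect on a median.

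Finally, imaging-manual or reader instructions not shown here may already settle the matter. If so, the definition that the SAP cites should still agree with them.

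**Conclusion.** Section 4.2.3.1 contradicts itself for a repeat scan with burden less than 20% above nadir, causal lesions stable or improved, and an additional new lesion (less clearly, additional non-target progression). It is wrong as written and worth correcting, but minor. The reach is site treatment decisions and the descriptive modified-RECIST PFS and response-duration summaries. The number of such scans, and any effect on those summaries, cannot be determined from the documents.

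A reader might infer that response rates are affected. For the primary tests and the PD-L1 positive test they are not: those use RECIST 1.1 by independent review (Sections 8.2.5.1 and 8.2.6), so alpha, power and the 14/135 boundary are untouched. For modified-RECIST ORR (secondary objective 4), no text says whether a CR or PR after confirmed PD counts, so no effect can be claimed.

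The conclusion rests on reading the 20% as an increase over nadir and on no precedence rule elsewhere in the documents.

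**What to change.** In Section 4.2.3.1, replace the not-confirmed sentence with: *PD is not confirmed if and only if none of the five scenarios listed below is present at the repeat scan.* Keep the permission to continue treatment after it. Word scenario 1 as an increase of both ≥ 20% and ≥ 5 mm from nadir. Apply the rule to both site and central modified-RECIST reads. Both directions of the condition are needed: 'only if' alone would leave a scan with no scenario present still unlabelled. With the full condition, all 12 combinations above get exactly one label: 2 not confirmed and 10 confirmed.

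The cost is one sentence, matching text wherever the imaging manual repeats the rule, and a check of repeat scans already read for the two patterns. No new scans are needed.

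The downside is that overlap scans a reader would have called not confirmed become progression. Modified-RECIST estimates may then be slightly less favourable, and those subjects could continue treatment only under the Section 7.1.2.6.3 exception. Any small-nadir scan that a reader would have called confirmed moves the other way.

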#### **4.2.3.2 Safety Endpoints**

The primary safety objective of this trial is to characterize the safety and tolerability of pembrolizumab (MK-3475) in subjects with HNSCC. The primary safety analysis will be based on subjects who experienced toxicities as defined by CTCAE criteria. Safety will be assessed by quantifying the toxicities and grades experienced by subjects who have received pembrolizumab (MK-3475), including serious adverse events (SAEs) and events of clinical interest (ECIs).

Safety will be assessed by reported adverse experiences using CTCAE, Version 4.0. The attribution to drug, time-of-onset, duration of the event, its resolution, and any concomitant medications administered will be recorded. AEs will be analyzed including but not limited to all AEs, SAEs, fatal AEs, and laboratory changes. Furthermore, specific immune-related adverse events (irAEs) will be collected and designated as immune-related events of clinical interest (ECIs) as described in Section 7.2.3.2.

#### **4.2.3.3 Planned Exploratory Biomarker Research**

Additional biomarker research to identify factors important for pembrolizumab (MK-3475) therapy may also be pursued. For example, tumor and blood samples from this study may undergo proteomic, genomic and transcriptional analyses. Additional research may evaluate factors important for predicting responsiveness or resistance to pembrolizumab (MK-3475) therapy and other immunologic targets.

Assays may include but are not be limited to:

